6.1 Statistical methodology

This study will be a randomized controlled trial of navigation bronchoscopy vs. CT-guided biopsy using a non-inferiority study design. The hypothesis of the study is that the diagnostic accuracy of EMN navigation bronchoscopy using the SuperDimension platform with F-Nav performed by interventional pulmonologists is non-inferior to the diagnostic accuracy of CT-guided biopsy performed by interventional radiologists. Eligible patients will be randomized on a 1:1 basis and the randomization will be stratified by the following two criteria within each center to provide balance between treatment arms on these features:

1. Location in the middle or outer third of the lung
2. Pre-test probability of malignancy (50% or less VS 51% or more)

Within each stratum, block sizes of 2 and 4 will be used to enhance blinding.

Though the primary analysis will use a Bayesian approach, the initial power analysis uses a Frequentist approach. We assume that a diagnostic accuracy for CT-guided biopsy is 90%. The non-inferiority margin is set at 10 percentage points, and one-sided type I error rate is set at 5%. Thus, if the true diagnostic accuracy for navigation bronchoscopy is lower than 80%, we will have 5% probability (type I error rate) to incorrectly conclude noninferiority. With this parameter setting a sample size of 112 per group will give approximately 80% power if the true diagnostic accuracies are 90% for both arms. Considering an attrition rate of 15%, the sample size is 129 per group (258 total). Large volume centers could be expected to enroll 50 patients per year, therefore 6 centers are necessary. One year recruitment plus one year follow-up represents 2 years of recruitment time. The noninferiority margin has been chosen based on the known pneumothorax rate of CT

CONFIDENTIAL

biopsy which is in excess of 10%, and after polling a number of clinicians who are involved in the diagnostic workup of patients with lung nodules, where this margin was considered reasonable.

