6.2 Analysis plan

Analytic populations

The analysis set will be the per-protocol (PP) population, which yields more conservative estimates for the noninferiority objective than the intention-to-treat (ITT) population. The ITT analysis will include every randomized subject assigning a treatment failure for those who drops out without the final data. The ITT analysis will be a secondary, sensitivity analysis.

Prior distribution

The probability of successful diagnostic accuracy for each treatment arm will be modeled with a Beta-Binomial distribution. A non-informative prior Beta (1,1) will be used for both treatment arms.

Interim analysis

No interim analysis is planned for this trial. Interim analyses typically assess for futility and efficacy stops regarding the primary outcome part-way through a trial. However, the primary outcome of diagnostic accuracy requires up to 12 months of radiographic follow-up in patients not determined to have malignant nodules by study biopsy. Therefore, an analysis of this outcome halfway through accrual could not be performed until one year after that enrollment midpoint was reached, at which time we expect enrollment to be complete for the entire planned accrual. An interim analysis of the primary endpoint is therefore impracticable. Interim analyses for safety endpoints are often commonly performed in investigations of new devices or novel interventions, but as both study procedures represent long-standing standard of care options for the tissue sampling of lung nodules, complications of these procedures themselves are not considered risks unique to this research. The primary risk to participation in this research involves patient privacy and confidentiality, any breach of which will be reported to the PI and appropriate regulators on an ongoing basis as described later in this protocol, which does not require interim analysis.

Final analysis

The final analysis will be conducted when data from all randomized patients are available (n=112 per group). The conclusion will be based on the final posterior distributions (n=112 each). We will conclude noninferiority of NB compared to CT if the estimated probability of inferiority is less than 5%. We will conclude superiority of NB if the estimated probability that NB is better than CT is higher than 95%.

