The median estimate and 95% credible interval will be given for the diagnostic accuracy for NB and for CT, as well as their difference. Additionally, we will estimate and report the probability that NB is non-inferior to CT and NB is superior to CT. These probabilities can be estimated using the posterior distributions of diagnostic accuracies.

Subgroup analysis:

CONFIDENTIAL

Pre-hoc analyses of subgroups will include the groups defined by the two stratification factors, expertise of radiologist or pulmonologists, etc... The full list of subgroup pre-hoc analyses will be defined in the statistical analysis plan which will be completed and signed off by the trial steering committee prior to final patient entry and prior to any prior full analysis of the data. To allow for comparison of diagnostic accuracy and yield differences across subgroups (e.g., middle vs outer third), logistic regression models with interaction with treatment group will be fit.

Operating characteristics

With the Bayesian paradigm, there is no type I error rate. We conducted a simulation study to determine appropriate threshold for noninferiority conclusion and superiority conclusion at the final analysis. The operating characteristics of the proposed design under various scenarios for the true unknown parameter distributions were evaluated and shown in the below table. In this simulation study, we first postulated the true distribution of the diagnostic accuracy using a Beta distribution, which gives the specific mean and standard deviation. For example, Beta(141, 35) is used to represent a distribution with mean 0.80 and standard deviation (sd) 0.03. We used 0.60, 0.70, 0.80, and 0.90 as the mean and 0.01 and 0.03 as the sd. However, because different standard deviations yielded similar results, we only present the results for sd=0.03. The simulation size is 10,000 and the available decision in the simulation is: conclude non-inferiority at final analysis (> -10%). The following table shows its probability under various scenarios.

Design characteristics with final 10% (0.95)

True CT Mean	True NB Mean	True State	Difference	Final analysis		
				NB is non-inferior	NB is superior	
0.7	0.6	Inferiority	-0.1		5.3	--
0.8	0.7	Inferiority	-0.1		4.7	--
0.9	0.8	Inferiority	-0.1		5.4	--
0.8	0.6	Inferiority	-0.2		--	--
0.9	0.7	Inferiority	-0.2		--	--
0.7	0.7	Non-inferiority	0.0		44.9	4.9
0.8	0.8	Non-inferiority	0.0		54.2	4.9
0.9	0.9	Non-inferiority	0.0		74.4	4.7

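### Allocation is stratified by nodule location and pre-test probability within center, but the primary Beta-Binomial ignores the strata: a small, assumed loss of precision, not a validity problem

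*Combined protocol and SAP*

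**What the plan says.** Section 6.1 (Statistical methodology) states that "the randomization will be stratified by the following two criteria within each center to provide balance between treatment arms on these features". The two criteria are location (middle or outer third of the lung) and pre-test probability (50% or less against 51% or more), in blocks of 2 and 4. The same section states that "a sample size of 112 per group will give approximately 80% power" when true accuracy is 90% in both arms, with a 10-point margin and one-sided 5% error.

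Section 6.2 (Analysis plan) gives the primary model: "The probability of successful diagnostic accuracy for each treatment arm will be modeled with a Beta-Binomial distribution". It adds: "A non-informative prior Beta (1,1) will be used for both treatment arms". Non-inferiority is concluded if the estimated probability of inferiority is below 5%. On that probability and the one for superiority, the plan says: "These probabilities can be estimated using the posterior distributions of diagnostic accuracies". No stratum, center or covariate term is stated for this decision, and no adjusted sensitivity analysis is stated.

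The stratification factors reappear only under Subgroup analysis, where "logistic regression models with interaction with treatment group will be fit". The full subgroup list is left to an SAP to be "completed and signed off by the trial steering committee prior to final patient entry". On calibration, the section says: "We conducted a simulation study to determine appropriate threshold for noninferiority conclusion and superiority conclusion at the final analysis".

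**The concern.** Stratified allocation removes part of the chance difference between arms when a stratifier predicts the outcome. An analysis of arm totals still counts that part as random variation, so its interval for the difference is wider than the design requires.

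Pre-test probability could well be prognostic here. Under the primary endpoint in section 4.8, malignant histology counts as a success at once. A benign nodule generally needs a specific benign finding and a year without malignancy, or matching surgical histology. Section 4.2 admits pre-test probabilities from 10% to 100%, so the two strata should differ in their share of malignant nodules.

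At stake is a modest amount of precision. It would matter mainly if the posterior probability landed close to 0.95. In that case, having no pre-specified adjusted result would invite a choice made after seeing the data.

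**Working it through.** **Inputs.** From sections 6.1 and 6.2: 112 per arm, accuracy 90% in both arms for power, 90% (CT) and 80% (bronchoscopy) for error at the margin, 10-point margin, Beta(1,1) per arm, posterior cut-off 0.95. Assumed: how far accuracy differs between pre-test strata, and the stratum shares.

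**1. Reproduce the plan.**
- n = (1.645 + 0.842)² × 2 × 0.9 × 0.1 / 0.10² = 111.3, so 112 per arm.
- Normal-approximation power: SE = sqrt(2 × 0.09/112) = 0.0401, and Φ(0.10/0.0401 − 1.645) = 80.2%.
- Exact enumeration of the Beta(1,1) rule at fixed true rates: power 80.1%, error at 90/80 5.3%.
- The plan's table gives 74.4% non-inferior plus 4.7% superior = 79.1% at 90/90, and 5.4% at 90/80. The two columns are exclusive: the last row is 1.3% + 98.7% = 100%.
- Section 6.2 describes the table as drawn with sd = 0.03, but only fixed rates reproduce it. Drawing true rates with sd 0.03 gives 11.2% error at 90/80 and 72.9% in total at 90/90.

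**2. Excess interval width.** Let p be the accuracy in a stratum and p̄ the overall accuracy.
- SE that the unadjusted analysis uses: SE_u = sqrt(2 × p̄(1 − p̄)/112).
- SE that stratified allocation delivers: SE_t = sqrt(2 × mean of p(1 − p)/112).
- Example, 82% and 98% in equal strata: mean p(1 − p) = (0.1476 + 0.0196)/2 = 0.0836, so SE_t = 0.0386. SE_u = 0.0401. The ratio is 1.04, so the interval is 4% too wide.

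**3. What the splits require.** Take malignancy shares at the middle of each stratum's range: 30% and 75.5%, a difference of 0.455. The accuracy gap needed between malignant and benign nodules is then split/0.455. Splits of 10, 16 and 20 points need gaps of 22, 35 and 44 points.

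**4. Exact comparison, 56 patients per arm per stratum.** The stratified rule uses Beta(0.5,0.5) per arm and stratum, weights the stratum differences by stratum share, and applies the same 10-point margin. Error is computed with a 10-point deficit in each stratum. The 0.953 column is an illustration, not a proposed cut-off.

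| Accuracy low/high stratum | Interval excess | Planned rule: power | Planned rule: error | Stratified at 0.953: power |
|---|---|---|---|---|
| 90/90 | 0% | 80.1% | 5.3% | 79.3% |
| 85/95 | 1% | 80.4% | 5.1% | 80.4% |
| 82/98 | 4% | 80.9% | 4.8% | 81.8% |
| 80/100 | 6% | 81.4% | 4.6% | 83.3% |

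The stratified rule's error is about 5.4–5.5% at an unchanged 0.95, and 5.1–5.2% at 0.953.

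**5. Unequal strata and block imbalance.** This was a simulation of 224 patients, 6 centers and blocks of 2 and 4, with 100,000 trials per scenario. Power at 0.953 against the planned rule:
- no split: 79.2 v 79.7% (equal strata);
- 20 points: 83.0 v 80.8% (equal strata), 83.3 v 80.8% (30% of patients in the low stratum);
- 70% in the low stratum: 79.7 v 80.1% at 10 points, 80.2 v 80.2% at 14 points.

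The net change ranges from −0.5 to +2.5 points.

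**6. Cross-check by a different method.** The normal approximation with 24 center-by-stratum cells compares unadjusted and stratified power for an assumed odds ratio per factor and center SD on the logit scale:
- OR 1.5, SD 0.2: 80.3 v 80.6%;
- OR 2, SD 0.3: 80.6 v 81.2%;
- OR 3, SD 0.5: 81.1 v 82.6%;
- OR 4, SD 0.7: 81.6 v 84.2%.

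Unadjusted error over these four falls from 4.9% to 3.9%.

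**The case against.** The strongest reply is that nothing here is an error. Section 6.1 stratifies in order to balance the arms, and allocation does that. The plan never promises an adjusted primary analysis. When the strata matter, planned power rises and error falls. The large splits are unsupported by any figure in the documents, and one of them needs 100% accuracy in a stratum. At a 10-point split the stratified rule gains almost nothing (80.1 v 79.9% with equal strata), and with no split it loses a little. It also covers only one of the stratifiers. Finally, the model, prior and decision rule are fixed in the protocol, so replacing them is more than SAP wording.

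Nearly all of this stands, and it limits both the severity and the remedy. A very fine cut-off is also fragile. At 80/100, a shift of 0.001 around 0.951 moves stratified power from 84.35% to 83.33%, almost entirely through one pair of outcomes. What the reply does not remove is that the plan has no pre-specified analysis matching its own randomisation, and that adding one as support is cheap.

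A reader might infer two stronger things. One is that ignoring the strata makes the primary analysis invalid or raises its error rate. The calculation shows the opposite: error moves from 5.3% down to 4.6%. The other is that the trial is underpowered for this reason. The planned rule keeps about 80% power in every scenario examined at the plan's 90% accuracy.

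A third idea is to keep the unadjusted model and relax its cut-off. At 82/98, a cut-off of 0.945 gives 82.6% power with 5.37% error, so part of the apparent gain is unspent error. With no split the same cut-off gives 5.83% error, so it is safe only if the split is known in advance.

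**Conclusion.** The point holds as a minor one of efficiency. The primary decision does not use the strata on which patients are randomised. The analysis is valid, meets its stated power, and is slightly conservative if the strata are prognostic. The cost is about 0 to 1 power point for weak or moderate effects, and about 2 to 2.5 points for large ones. These figures rest on assumed accuracy splits, stratum shares and center variation, none of which the documents give. If pre-test probability is not prognostic, there is nothing to gain. No change in sample size or margin follows.

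**What to change.** Before the last patient is entered and before any unblinded analysis, pre-specify an analysis stratified by pre-test probability. For example, use Beta(0.5,0.5) per arm within each stratum, which keeps the total prior weight per arm at 2 pseudo-observations, as with Beta(1,1). Combine the strata by share into one marginal risk difference, keep the 10-point margin, and report it beside the unadjusted Beta-Binomial.

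- **As a supporting analysis:** this needs SAP text only. The stratum is already recorded at randomisation, and the primary decision is untouched.
- **As the primary analysis:** this is a protocol amendment, with the approvals that section 9.1 requires. The operating characteristics must be rerun at fixed true rates over plausible splits and stratum shares. The cut-off must then be set so that error at 90/80 is no higher than the planned rule's (5.3% exact with no split). An unchanged 0.95 does not meet this, and no particular value such as 0.953 should be fixed before the rerun. The superiority rule should be rechecked in the same run.
- **A model that also adjusts for location and center:** sensitivity analysis only. About 22 non-diagnostic results are expected (224 × 10%), so it leans on its prior. A logistic version with N(0, 2.5²) priors had simulated error of 6.8–7.3% at 0.95 (5,000 trials per scenario).

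The cost is a little more analysis work, and an amendment if the analysis becomes primary. In that case, if pre-test probability is not prognostic, there is no gain and up to about 0.5–0.8 power points may be lost (79.2 v 79.7% simulated, 79.3 v 80.1% exact, at 0.953). Location and center remain unadjusted in the conjugate version.

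### Subgroup differences are to be compared by a logistic interaction (a ratio of odds ratios), while the margin, decision rule and primary summary are percentage-point differences; subgroup differences in points should be specified.

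*Combined protocol and SAP*

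**What the plan says.** The trial is built on the difference scale. Protocol section 6.1 states: "The non-inferiority margin is set at 10 percentage points". The final-analysis rule in section 6.2 reads "We will conclude noninferiority of NB compared to CT if the estimated probability of inferiority is less than 5" per cent, with inferiority meaning a difference beyond -10 points. The operating-characteristics table is indexed by the difference in accuracy. The primary report gives a median and 95% credible interval for each arm and for their difference.

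The subgroup paragraph of section 6.2 states its aim as "To allow for comparison of diagnostic accuracy and yield differences across subgroups (e.g., middle vs outer third", and then the method: "logistic regression models with interaction with treatment group will be fit". It names the two stratification factors (lung third and pre-test probability) and operator expertise, and leaves the list open. Only the full list of subgroups is deferred to a later statistical analysis plan, to be signed off before final patient entry. The paragraph does not mention subgroup differences in points, subgroup posteriors, conversion of the logistic results to points, or how the interaction is to be read.

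**The concern.** A treatment-by-subgroup term in a logistic model asks whether the odds ratio is the same in both subgroups. A reader of this trial will want to know whether NB minus CT in points is the same, because that is what the margin refers to. The two questions have different answers when two conditions hold together: NB differs from CT, and CT accuracy is not the same in the two subgroups.

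A small interaction term could then be taken as a sign that the overall difference applies to, say, both middle-third and outer-third nodules, when the loss in points is much larger in one of them. At stake is the reading of a supportive analysis.

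**Working it through.** **The plan's own figure.** Section 6.1 says "a sample size of 112 per group will give approximately 80% power if the true diagnostic accuracies are 90% for both arms". On the difference scale, with one-sided 5% and a 10-point margin, n = (1.645 + 0.842)² × 2 × 0.9 × 0.1 / 0.10² = 111.3, so 112 per group; power at 112 is 80.2%. The figure reproduces, which confirms that the design works in percentage points.

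**Inputs that are not in the documents.** Subgroup sizes and CT accuracy by lung third or by pre-test probability are not given. Section 3.1 gives CT yield of about 90% in general and 70-80% in nodules below 1.5 cm. That is a size effect, and size is not a named subgroup. The subgroup rates below are therefore assumptions. The 56 patients per cell are 112 per arm split equally.

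**Step 1: a zero logistic interaction, converted to points.** Take the odds ratio at the margin: (0.80/0.20) / (0.90/0.10) = 4/9 = 0.444. Hold it constant, so that the interaction is exactly zero. For CT accuracy c, NB odds = 0.444 × c/(1 - c), and NB accuracy = odds/(1 + odds).

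| CT accuracy | NB accuracy | NB minus CT (points) |
|---|---|---|
| 95% | 89.4% | -5.6 |
| 90% | 80.0% | -10.0 |
| 80% | 64.0% | -16.0 |
| 75% | 57.1% | -17.9 |

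With a milder odds ratio of 0.630 (90% to 85%), the differences are -2.7, -5.0, -8.4 and -9.6.

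**Step 2: detecting a real difference in points.** Assume CT/NB of 95/95 in one subgroup (0 points) and 80/60 in the other (-20 points), 56 per cell.

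- Log-odds: effect = ln(0.6/0.4) - ln(0.8/0.2) = -0.981. Variance = [2/0.0475 + 1/0.16 + 1/0.24]/56 = 0.938, so SE = 0.968 and |z| = 1.01. Power of a two-sided 5% test is about 17%.
- Difference: effect = -0.20. Variance = (2 × 0.0475 + 0.16 + 0.24)/56 = 0.00884, so SE = 0.094 and |z| = 2.13. Power is about 57%.

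Simulation of 200,000 trials, adding 0.5 to each count on the log-odds scale, gives 14% and 57%. In the zero-interaction case of 95/89.4 against 75/57.1, it gives 2.8% on log-odds and 24% on the difference scale.

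**Step 3: how far this can go when the trial passes.** Assume overall CT 90% and a low-accuracy subgroup (CT 70-80%, holding 20-40% of patients, in the combinations that are arithmetically possible). With a constant odds ratio and a true overall difference of -5 points, that subgroup lies at -8.7 to -14.0 points. Under the Beta(1,1) rule with 112 per arm, a true -5 passes in about 31% of trials and a true -8 in about 12%. In terms of observed results, with CT at 101/112 the rule passes only down to -2.7 points. A constant odds ratio then puts the low-accuracy subgroup at about -5 to -7, inside the margin.

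**Step 4: sparse cells.** An ordinary maximum-likelihood interaction estimate does not exist if a cell has no failures. With all four cells at 90%, the chance of at least one such cell is 1 - (1 - 0.9^56)^4 = 1.1%. With one cell at 95% it is about 6%, and with two about 11%.

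**The case against.** Section 6.2 says only that models will be fitted. It sets no threshold, no consistency criterion and no rule for non-inferiority within a subgroup. For a two-level factor, a logistic model with treatment, subgroup and their interaction reproduces all four observed proportions, so both point differences can be recovered from it. This stands: the gap is an unspecified reporting scale, and the model itself does not hide anything.

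The most striking scenarios are not ones in which the trial would normally succeed. With equal subgroups, 95/89.4 against 75/57.1 is (-5.6 - 17.9)/2 = -11.75 points overall and passes in about 2% of trials. The pair 95/95 against 80/60 is -10 points overall, where the protocol's own table puts the chance of passing near 5%. If both arms are truly 90% in every subgroup, the two scales agree. This also stands.

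A reader might infer more than the documents support:

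- That a formal test would certify consistency. None is planned.
- That the model would often report heterogeneity where the point difference is constant. At 56 per cell, the log-odds test rejects in about 4% of trials for 95/90 against 80/75 and about 6% for 95/85 against 80/70, close to nominal.
- That the logistic estimate would often fail at about 90% accuracy. Step 4 shows that this is uncommon unless some cells are nearer 95%.
- That CT accuracy is known to differ by stratum. Section 6.1 gives balance as the reason for stratifying and does not call the factors prognostic.

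Finally, power is low on either scale, so changing the scale does not make a null interaction reassuring. That argues for estimates with intervals.

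**Conclusion.** The mismatch of scale is real. The only named method for comparing subgroup differences works on odds ratios, while everything else in the trial is in percentage points, and nothing in section 6.2 closes the gap. A zero interaction is compatible with -5.6 points in one subgroup and -16 in another, and a real 20-point contrast can be detected far less often on log-odds (about 14%) than on the difference scale (about 57%). These sizes rest on assumed subgroup rates and equal cells. They need both a true NB deficit and unequal CT accuracy; a subgroup beyond the margin under a constant odds ratio needs an overall deficit of roughly 5 points or more. The point concerns a supportive analysis, and the primary conclusion does not depend on it.

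**What to change.** In the subgroup paragraph of section 6.2, or in the later statistical analysis plan that it announces, state that:

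- each prespecified subgroup will have the posterior median and 95% credible interval of NB minus CT in percentage points, from the same Beta(1,1)-binomial model as the primary analysis;
- the posterior of the difference between the subgroup differences will be reported in the same way;
- both are read as estimates with intervals, and not as a pass/fail consistency test;
- the logistic interaction model is kept as supportive.

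The Beta(1,1) posteriors also remain defined if a cell has no failures. The cost is a few lines of text and code, with no new data and no change to the sample size or the primary analysis.

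### The *NB is non-inferior* column of the operating-characteristics table counts only trials that are non-inferior but not superior, so as labelled it understates the probability of concluding non-inferiority in eight rows

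*Combined protocol and SAP*

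**What the plan says.** Section 6.2 (Final analysis) sets the rule: "We will conclude noninferiority of NB compared to CT if the estimated probability of inferiority is less than 5"%. Superiority is a separate conclusion, reached when the posterior probability that NB beats CT exceeds 95%. Nothing says that a trial meeting the superiority rule ceases to count as non-inferior. On the prior: "A non-informative prior Beta (1,1) will be used for both treatment arms". The decision is based on 112 patients per arm.

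Section 6.2 (Operating characteristics) reports 10,000 simulated trials per scenario. It says that the true accuracies follow Beta distributions and that results are shown for sd 0.03. The only decision it names is to "conclude non-inferiority at final analysis (> -10%). The following table shows its probability under various scenarios". The table has two result columns, *NB is non-inferior* and *NB is superior*. Neither the headings nor the text says that the columns exclude each other.

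Section 6.1 gives the frequentist calculation: "a sample size of 112 per group will give approximately 80% power if the true diagnostic accuracies are 90% for both arms".

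**The concern.** The column behaves in a way that its description does not allow. As NB's true advantage grows, the printed probability of concluding non-inferiority falls: 74.4% at 0.9/0.9 (CT/NB), 31.7% at 0.8/0.9 and 1.3% at 0.7/0.9. A probability of clearing a margin of -10 points should rise with the true difference.

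This table is the only evidence in the plan on how the Bayesian primary rule performs, and Section 6.2 says that the simulation was used to set the decision thresholds. A reader who takes the 0.9/0.9 row at face value will put the chance of success at the design point at 74.4%, and may conclude that the Bayesian rule misses the power target in Section 6.1.

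**Working it through.** **Inputs.** From Section 6.2: 112 per arm, Beta(1,1) priors, margin 10 points, posterior threshold 95% for both conclusions. From Section 6.1: 90% accuracy in both arms, one-sided 5%, about 80% power.

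**1. Section 6.1 reproduces.** The standard error of the difference is √(2 × 0.9 × 0.1 / 112) = 0.0401. Power is Φ(0.10/0.0401 − 1.645) = Φ(0.85) = 80.2%.

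**2. Superiority is nested in non-inferiority.** For any data, P(NB − CT > −0.10) is at least P(NB − CT > 0). If the second exceeds 0.95, so does the first. Enumerating all 113 × 113 pairs of counts confirms it: no outcome meets superiority without meeting non-inferiority. P(conclude non-inferiority) therefore cannot be smaller than P(conclude superiority). The printed table breaks this in four of the five superiority rows: 43.7 against 53.0, 31.7 against 67.8, 4.8 against 95.1, and 1.3 against 98.7.

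**3. What the column contains.** With x successes, each arm's posterior is Beta(1 + x, 113 − x). Every outcome pair is classified by the two rules and weighted by its binomial probability, with the true accuracies fixed at the listed means. All entries are in %.

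| CT / NB | Printed NI | Printed superior | Sum of printed | Exact: NI, not superior | Exact: superior | Exact: NI total |
|---|---|---|---|---|---|---|
| 0.7 / 0.7 | 44.9 | 4.9 | 49.8 | 45.2 | 4.9 | 50.1 |
| 0.8 / 0.8 | 54.2 | 4.9 | 59.1 | 54.6 | 4.8 | 59.4 |
| 0.9 / 0.9 | 74.4 | 4.7 | 79.1 | 75.0 | 5.0 | 80.1 |
| 0.6 / 0.7 | 47.0 | 46.5 | 93.5 | 46.0 | 47.5 | 93.5 |
| 0.7 / 0.8 | 43.7 | 53.0 | 96.7 | 43.6 | 53.1 | 96.7 |
| 0.8 / 0.9 | 31.7 | 67.8 | 99.5 | 31.9 | 67.6 | 99.5 |
| 0.6 / 0.8 | 4.8 | 95.1 | 99.9 | 4.9 | 95.1 | 100.0 |
| 0.7 / 0.9 | 1.3 | 98.7 | 100.0 | 1.4 | 98.6 | 100.0 |

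The printed column matches *non-inferior and not superior* within 1.0 point in every row. It misses the total by about 5 to 99 points.

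**4. Inferiority rows.** At a true difference of −0.1 the exact superiority probability is 0.1% or less, so the total (5.1, 5.2, 5.3) and the exclusive figure (5.0, 5.1, 5.2) nearly coincide. Both agree with the printed 5.3, 4.7 and 5.4. At −0.2 everything is below 1%.

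**5. Effect of the stated sd.** Step 3 fixes the truth, whereas Section 6.2 states sd 0.03. Drawing both true accuracies from Beta distributions with that sd (beta-binomial weights) gives the following:

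- At 0.9/0.9: 60.1% non-inferior but not superior, 12.8% superior, 72.9% in total.
- Totals in the five superiority rows: 89.7, 93.0, 97.0, 99.6 and 99.9.
- Totals in the three rows at −0.1: 8.8, 9.5 and 11.2, against the printed 5.3, 4.7 and 5.4.

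The printed table therefore fits a truth fixed at, or very close to, the means. It does not fit sd 0.03 in both arms.

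**The case against.** The strongest reply is that nothing has been miscalculated. The two columns are valid as exclusive outcomes, the totals follow by adding them, and in the superiority rows the sums of 93.5 to 100.0 hint at the split. A reader who sees 1.3 beside 98.7 is unlikely to think that NB will fail. Section 6.1's 80% is also a frequentist figure and need not equal an average over uncertain true rates.

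Most of this stands. The gaps of up to 99 points are simply the adjacent column. A reader might infer that the simulation is wrong by that much, or that the Bayesian rule has only 74.4% power and so contradicts Section 6.1. The documents support neither: the counts reproduce, and 74.4% is not the probability of the decision that Section 6.2 defines.

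What does not stand is that the label is harmless. The text gives the column a different meaning from the one it has. At 0.9/0.9, the row that matters for design, the columns sum to 79.1, so nothing prompts a reader to add them.

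Nor does the stated sd rescue the column. The 72.9% total at sd 0.03 happens to lie near 74.4%, but superiority would then be 12.8% rather than 4.7%, and the superiority-row totals would be 89.7 to 99.9 rather than 1.3 to 47.0.

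**Conclusion.** The column is mislabelled. Under the rule in Section 6.2, the probability of concluding non-inferiority is the sum of the two printed columns. The printed entry falls short of it by the superiority entry in all eight non-inferiority and superiority rows: by 4.7 points at the design point, and by 46.5 to 98.7 points where NB is truly better. That the column cannot be the stated probability follows from the nesting of the two rules and needs no distributional assumption. Identifying it as *non-inferior but not superior* rests on 112 per arm, Beta(1,1) priors and true accuracies fixed at the listed means.

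The sample size, margin, decision rule and five inferiority rows are not affected by the labelling. It may be tempting to say that the sums show the Bayesian rule delivering the 80% of Section 6.1. The documents do not yet support that: fixed truth gives 80.1% at 0.9/0.9, but the stated sd of 0.03 in both arms gives about 72.9%.

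**What to change.** Relabel the column *non-inferior but not superior*. Add a column for the total probability of concluding non-inferiority, and mark superiority as a subset of that total. In the table's row order, from 0.7/0.7 to 0.7/0.9, the sums of the printed columns are 49.8, 59.1, 79.1, 93.5, 96.7, 99.5, 99.9 and 100.0. State in the text that superiority implies non-inferiority.

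Before setting 79.1% beside the figure in Section 6.1, check the simulation code for the sd used. If the truth was fixed at or very near the means, correct the sd description. If sd 0.03 in both arms was intended, rerun and replace the table; the −0.1 rows would then change as well.

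The relabelling and totals need only the existing output. Checking the sd is a look at the code and, at most, one rerun. Neither change alters the design.
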